4.12.1.3 Definition of Serious Adverse Event (SAE)

AEs fall into the categories "non-serious" and "serious.".

An SAE is any untoward medical occurrence that, at any dose:

- Results in death
- Is life-threatening
- Requires subject hospitalization or prolongation of existing hospitalization
- Results in persistent or significant disability and/or incapacity
- •Results in a congenital anomaly or birth defect
- 4.12.1.4 Severity

All AEs will be graded for severity, if possible, by the Common Terminology Criteria for Adverse Events (CTCAE) version 4.03 or later.

4.12.1.5 Relationship to Investigational Product

Association or relatedness to the investigational product will be graded as either "definitely related", "probably related", "possibly related", "unlikely related", or "not related".

AEs with causal relationship to IMP "definitely related", "probably related", "possibly related" will be considered as 'Related' AEs; AEs with causal relationship to IMP "unlikely related", or "not related" will be considered as 'Not Related' AEs

4.12.1.6 Adverse Event of Special Interest (AESI)

Certain adverse events, spontaneously reported by a subject, will be documented in more detail as part of the analysis to determine any abuse potential of nalbuphine.

The AESI section of the AE eCRF provides for recording the following details about any events

meeting the characteristics described above:

- Additional Subject's Narrative, i.e. a description of the AE event in the subject's own words;
- Investigator comments and/or assessment;
- The estimated time between the subject's most recent dose prior to the AE, and the onset time of that AE (e.g., X minutes or Y hours between preceding dose and AE onset); such an estimate is directly collected from eCRF;
- Prior history of this symptom or event.
- 4.12.1.7 Handling of AEs partial dates

If medication start date is missing or partial, the dates will be compared as far as possible with the date of first dose of study medication in both Treatment Periods to assess if the AE is treatment emergent with respect to one of the two treatment periods.

4.12.1.8 Analysis of AEs

All AEs will be listed as defined in SAP section 4.2.4. The following information will be included in the listings: Description of AE, System Organ Class (SOC), Preferred Term, onset date, end date, TEAE status, CTCAE Severity Grade, Seriousness (Yes/No and seriousness criteria), Outcome, Relationship to Study Treatment, Action Taken with Study Treatment, Other Actions Taken, AE of Special Interest (Yes/No).

All AESI will be listed separately following definition in SAP section 4.2.4. The following information will be included in the listings: Description of AE, System Organ Class (SOC), Preferred Term, onset date, end date, TEAE status, AE of Special Interest (Yes/No), Subject's Narrative, Investigator's Comments, onset datetime, estimated time between last dose and onset of AESI, prior history of the symptom or event.

The TEAEs will be presented using summary tables as defined in SAP section 4.2.5, in general, in TEAEs summaries number of subjects with an event will be printed as well as number of events.

Summary tables:

• Patient Overall Summary of TEAEs; this table will include following summaries:

• Any TEAEs

- Any related TEAEs
- Any Serious TEAEs
- Any related Serious TEAEs
- Any treatment emergent AESIs
- Any related treatment emergent AESIs
- o Any serious treatment emergent AESIs
- o Any related serious treatment emergent AESIs
- Any Grade 3 or higher TEAEs
- Any Related Grade 3 or higher TEAEs
- Any TEAEs leading to IMP interruption
- Any Related TEAEs leading to IMP interruption
- Any TEAEs leading to IMP withdrawn
- o Any Related TEAEs leading to IMP withdrawn
- Any FATAL TEAEs
- Any Related FATAL TEAEs
- TEAEs by SOC and PT
- Related TEAEs by SOC and PT
- TEAEs by SOC and PT and Worst CTCAE Grade
- Related TEAEs by SOC and PT and Worst CTCAE Grade
- Serious TEAEs by SOC and PT
- Related Serious TEAEs by SOC and PT
- TEAEs Leading to IMP interruption by SOC and PT
- Related TEAEs Leading to IMP interruption by SOC and PT
- TEAEs Leading to IMP withdrawn by SOC and PT
- Related TEAEs Leading to IMP withdrawn by SOC and PT
- Fatal TEAEs by SOC and PT
- Related TEAEs by SOC and PT
- Serious AEs Key Subject Information
- Adverse Events with Outcome of Death Key Patient Information

Adverse events will be coded using the Medical Dictionary for Regulatory Activities (MedDRA) Version 22.0 or higher.

4.12.2 Deaths, Serious Adverse Events, and Other Significant Adverse Events

Reporting of Deaths, Serious Adverse Events and other significant Adverse Events is described in the above section 4.11.1.1.

4.12.3 Clinical Laboratory Evaluation

By subject listings of safety laboratory data will be provided as defined in SAP section 4.2.4. Abnormal safety laboratory data will also be listed separately.

4.12.4 Safety laboratory data will be summarized by actual treatment received and visit as defined in SAP section 4.2.5. Pregnancy

Pregnancy test results will be listed as defined in SAP section 4.2.4.

4.12.5 Vital Signs

By subject listings of vital signs will be provided as defined in SAP section 4.2.4.

Vital signs will be summarized by actual treatment received and visit as defined in SAP section 4.2.5.

4.12.6 Physical Examination

By subject listings of Physical Examination will be provided as defined in SAP section 4.2.4.

4.12.7 ECG

By subject listings of ECG data will be provided as defined in SAP section 4.2.4.

ECG data will be summarized by actual treatment received and visit as defined in SAP section 4.2.5.

4.12.8 Spirometry

Spirometry will not be executed at the end of treatment period 1 (Visit 6), therefore the screening spirometry results will be used as study baseline for both period 1 and period 2.

By subject listings of Spirometry results will be provided as defined in SAP section 4.2.4.

Spirometry results will be summarized by actual treatment received and visit as defined in SAP section 4.2.5.

4.12.9 Swallow Test

By subject listings of Swallow Test data will be provided as defined in SAP section 4.2.4.

4.12.10 SOWS

By subject listings of SOWS results will be provided as defined in SAP section 4.2.4.

SOWS results will be summarized by actual treatment received and study day as defined in SAP section 4.2.5.

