BMI = body mass index; PK = pharmacokinetic; AE = adverse event; conmeds = concomitant medications

- = Investigational product administration in each treatment period will be separated by a washout interval of 2 weeks between dosing.
- 2 = Follow-up will occur 14±2 days after the last administration of investigational product.
- 3 = First dose of investigational product for Treatment Period 1 is taken the evening of Day 1 after removal of the cough monitor.
- 4 = Last dose of investigational product for Treatment Period 1 is the morning dose of Day 22.
- 5 = Electrocardiogram (ECG) to be recorded prior to blood sampling when possible at scheduled visits where PK and/or clinical labs are obtained. Subjects should be in the supine position for at least 5 minutes prior to obtaining ECGs with all 3 tracings captured within a 3-5 minute window.
- 6 = Includes heart rate, blood pressure, respiratory rate, body temperature, and pulse oximetry. Vital signs should be taken prior to blood sampling and measured after the subject has been seated for at least 5 minutes.
- 7 = Performance of spirometry should adhere to ATS/ERS guidelines; required as part of meeting inclusion criterion #2.
- 8 = A negative urine pregnancy test will be confirmed prior to randomizing any female subjects of childbearing potential.
- 9 = Blood and urine samples for clinical laboratory testing should be obtained after 8 hours of fasting whenever possible. Clinical chemistry, hematology, urinalysis, and coagulation will be assessed.
- 10 = Baseline values for the purposes of the statistical analysis of treatment effect on daytime cough frequency during that crossover period. First dose of investigational product on Treatment Day 1 will be taken after removal of the cough monitor.
- 11 = Monitor will be placed on the subject by site staff at the end of the visit.
- 12 = Digital cough monitor hookup (24-hour recording); monitor will be worn until the evening of the following day in order to obtain at least a full 24-hour recording period of cough frequency. At the end of each recording session, the monitor will be removed at home by the subject prior to bedtime. On Treatment Day 1, the monitor will be removed prior to taking the first dose of investigational product. Subject to be provided with appropriate shipping material to return monitor for downloading of cough data (after removal).
- 13 = Administered on paper for screening; required as part of meeting inclusion criterion #6.

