3.2.3.10 Subjective Opiate Withdrawal Scale (SOWS)

Subjects will complete the SOWS on a daily basis for 14 days following the last dose of investigational product in each treatment period. Any subject discontinued from investigational product, prior to completion of the study, will also complete the SOWS daily for the 14 days following the last dose of investigational product (unless consent is withdrawn). The SOWS is a self-administered scale for grading opioid withdrawal symptoms.

The SOWS is provided in Protocol Appendix 4. Subjects will complete the SOWS via the study specific e-diary.

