4.2.2 Relative Study Day

4.2.2.1 Relative Study Day in Treatment Period 1

In Treatment Period 1, Study Day 1 is defined as the date of first investigational medicinal product (IMP) intake occurring on Treatment Period 1.

In Treatment Period 1, other study days are defined relative to the Study Day 1 as follow:

• assessments taken before the Treatment Period 1 first IMP administration:

Relative Study Day = assessment date - Treatment Period 1 first IMP intake date

• assessments on or after the repeat administration:

Relative Study Day = assessment date - Treatment Period 1 first IMP intake date + 1.

As soon as the first IMP intake occurs on Treatment Period 2, then the rules outlined in section 4.2.2.2 will apply.

4.2.2.2 Relative Study Day in Treatment Period 2

In Treatment Period 2, Study Day 1 is defined as the date of first IMP intake occurring on Treatment Period 2.

In Treatment Period 2, other study days are defined relative to the Study Day 1 as follow:

• assessments taken on or after Treatment Period 1 Visit 6 (Follow-up) and before the Treatment Period 2 first IMP intake:

Relative Study Day = assessment date - Treatment Period 2 first IMP intake date

• assessments on or after the repeat administration:

Relative Study Day = assessment date - Treatment Period 2 first IMP intake date + 1.

4.2.2.3 Relative Study Day at Visit 6

In most instances, the baseline visit for Treatment Period 2 will occur on the same calendar day as the Follow-up Visit 6 for Treatment Period 1; in this case, relative Study Day at Visit 6 will be calculated for Treatment Periods 1.

In the instance that baseline visit for Treatment Period 2 will occur on a different calendar day as the Follow-up Visit 6 for Treatment Period 1, then rules outlined in section 4.2.2.1 will apply to Follow-up Visit 6 for Treatment Period 1, while rules outlined in section 4.2.2.2 will apply to baseline visit for Treatment Period 2.

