4.2.4 Data Listings

All original and derived parameters will be listed.

Listings will include both scheduled and unscheduled measurements; such measurements will appear in chronological order together with the scheduled time points.

All listings will be sorted by sequence (i.e. Arm 1: NAL-ER + Placebo; Arm 2: Placebo + NAL-ER), subject number and time (visit); actual treatment received at timepoint will always be displayed, as appropriate. Study baselines will be flagged in listings.

Unless otherwise specified, relative study day will be provided for each date, please refer to Section 4.2.2 for derivation of relative study days. Study days relative to Treatment Period 1 will be printed as 'TP1:XX' (where XX stays for a particular study day); similarly, study days relative to Treatment Period 2 will be printed as 'TP2:XX' (where XX stays for a particular study day). In most instances, the Baseline visit for Treatment Period 2 will occur on the same calendar day as the Follow-up Visit 6 for Treatment Period 1; in this case, 'TP1:XX' will be printed.

Unless otherwise specified, listings will be presented based on all screened subjects; Screen Failure subjects will be included as well under 'Screen Failure:'.

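### The SOWS summary is indexed by study day from first dose, although the scale is collected from last dose, so early stoppers are misaligned with completers

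*SAP*

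**What the plan says.** **Collection.** Protocol 8.4.10 and SAP 3.2.3.10 tie the scale to the last dose of each treatment period. SAP 3.2.3.10 extends this to anyone who stops early, who "will also complete the SOWS daily for the 14 days following the last dose of investigational product" unless consent is withdrawn. Under Protocol 6.2 and 6.3 the last planned dose is the morning of Day 22 and entries begin on Day 23.

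**Tabulation.** SAP 4.12.10 reads: "SOWS results will be summarized by actual treatment received and study day as defined in SAP section 4.2.5". Section 4.2.5 sets the treatment columns and display rules but defines no study day. The listing section (4.2.4) shows where the definition sits: "please refer to Section 4.2.2 for derivation of relative study days".

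**Definition.** SAP 4.2.2 gives one rule per period: "In Treatment Period 1, Study Day 1 is defined as the date of first investigational medicinal product (IMP) intake", and "In Treatment Period 2, Study Day 1 is defined as the date of first IMP intake occurring on Treatment Period 2". Neither document defines a variable for days since last dose.

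**Change of period.** SAP 4.2.2.1 adds: "As soon as the first IMP intake occurs on Treatment Period 2, then the rules outlined in section 4.2.2.2 will apply". Section 4.2.2.2 also puts assessments from Visit 6 up to the first Period 2 intake on the Period 2 clock. Sections 4.2.2.3 and 4.2.5 keep Visit 6 itself with Period 1, but neither mentions diary entries made after it. Protocol Table 1 sets the visit window: "Follow-up will occur 14±2 days after the last administration of investigational product".

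**The concern.** A withdrawal scale is informative as a profile over time since the drug was stopped. If the rows count from the start of dosing, the profile is right only for subjects who all stop on the same day. Early stoppers' first days off drug fall into rows holding few other subjects. Their last days may be averaged with completers' first days.

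Early stops are foreseeable: Protocol 6.5 says that gastrointestinal and CNS effects tend to come early and may limit treatment. Safety is a primary objective, and Protocol 6.6 relies on daily SOWS reporting to address physical dependence. Study day is also a defined SAP term, so a programmer who follows the text will build the misaligned table.

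A smaller question arises at the change of period. Period 1 entries can still be due after Period 2 dosing has begun, and the SAP does not say which treatment they describe.

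**Working it through.** **Inputs**
- Last planned dose on Day 22, with 14 daily entries starting on Day 23 (Protocol 6.2, 6.3.1).
- Study day counted from first intake of the period (SAP 4.2.2).
- Visit 6 on Day 36 ± 2, that is Day 34 to Day 38 (Protocol Table 1), usually the same day as the Period 2 baseline (Protocol 6.3.1).
- First Period 2 dose on the evening after the baseline visit (Protocol Table 2, footnote 3).

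**Step 1: the plan's own window.** 22 + 1 = 23 and 22 + 14 = 36. Completers fall on Days 23–36, in agreement with the protocol, and for them study day and off-drug day match one to one.

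**Step 2: early stoppers.** With last dose on Day D < 22, entries run from D + 1 to D + 14.
- Rows shared with completers: (D + 14) − 23 + 1 = D − 8, or zero if that is negative.
- Within a shared row, the early stopper is 22 − D days further from the last dose than the completers.

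| Last dose (D) | Study days of entries | Entries in completers' rows | What is averaged together |
|---|---|---|---|
| 8 | 9–22 | 0 | nothing |
| 9 | 10–23 | 1 | off-drug day 14 with completers' day 1 |
| 10 | 11–24 | 2 | off-drug days 13–14 with completers' days 1–2 |
| 15 | 16–29 | 7 | off-drug days 8–14 with completers' days 1–7 |
| 21 | 22–35 | 13 | off-drug days 2–14 with completers' days 1–13 |

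For D = 10, 14 − 2 = 12 entries fall outside the completers' rows. The values of D are illustrative, and each row assumes that all 14 entries are made. The same arithmetic applies on the Period 2 clock.

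**Step 3: change of period, with Visit 6 and the Period 2 baseline on one day.** With Visit 6 on Day V, the first Period 2 dose is on Day V + 1. An entry on Day x ≥ V + 1 becomes Period 2 Day x − (V + 1) + 1 = x − V.

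| Visit 6 | First Period 2 dose (Period 1 count) | Entries relabelled |
|---|---|---|
| Day 34 | Day 35 | Day 35 becomes Period 2 Day 1 and Day 36 becomes Day 2: 2 of 14 |
| Day 35 | Day 36 | Day 36 becomes Period 2 Day 1: 1 of 14 |
| Day 36 | Day 37 | none if 4.2.2.3 governs; the Day 36 entry becomes Day −1 if 4.2.2.2 is read literally |
| Day 37 or 38 | Day 38 or 39 | none |

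**Step 4: after the change proposed below.** Entry date minus last intake date gives 1 to 14 for every subject, whatever D is. With attribution to the period just ended, 0 of 14 entries change treatment.

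**The case against.** **The display is descriptive and the data survive.** No formal safety testing is planned, and by-subject listings keep the information needed to realign the entries. This is true and limits the harm, but a listing is not a prespecified summary.

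**Withdrawal is captured elsewhere.** A reader might infer that this table is the trial's only summary of opioid withdrawal. It is not. Withdrawal is one of the categories of adverse events of special interest in Protocol 10.2.3. SAP 4.12.1.8 summarises those events and lists the estimated time from last dose to onset. The table is the only planned summary of the SOWS itself.

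**Completers are aligned.** This is correct. Dilution of their rows is probably small; the main loss is the scattering of early stoppers.

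**The change-of-period problem is an edge case.** Two relabelled entries require Visit 6 on its earliest permitted day. Dosing would then start on Day 35, which is 35 − 22 = 13 days after the last dose, whereas Table 1 footnote 1 gives a two-week interval between dosing; the window and that footnote need reconciling. The e-diary is also collected at Visit 6 and handed out again for Period 2, so it is not certain that Period 1 entries continue. These limits stand.

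**The treatment column may not change.** A reader might infer that relabelled entries are charged to the Period 2 treatment and so blur the comparison of NAL ER with placebo at the end of washout. The documents do not support that. Section 4.2.2 changes the day label; 4.2.5 gives no rule for washout diary entries, and 3.2.3.10 ties them to the period just ended. Relabelled entries would leave the Day 35–36 rows for Period 2 Days 1–2, where almost no SOWS data are scheduled. What remains is a missing attribution rule.

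**Conclusion.** The point holds for the row index. SAP 4.12.10 applies a first-dose clock to a scale collected on a last-dose clock. Anyone stopping before Day 22 is displaced by 22 − D days, with no overlap with completers for D of 8 or less and 2 of 14 entries shared for D = 10. The SOWS table cannot show the withdrawal time course for early stoppers. This rests on reading study day in 4.12.10 as the term defined in 4.2.2, the only definition available.

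The change-of-period point is secondary: one or two of 14 entries when Visit 6 falls on Day 35 or 34 and doubles as the baseline, provided that diary entries continue, plus an ambiguity over a visit-day entry.

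The number of subjects affected cannot be fixed from the documents. A reader might take 60 − 44 = 16 planned non-completers as the count. That is only a loose upper bound: it can include people who withdraw consent, from whom no SOWS is required, and people who finish Period 1 dosing and leave during washout, whose entries are aligned. SAP 4.14 and 4.15 also report that recruitment stopped before the planned total.

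**What to change.** In SAP 4.12.10:
1. Replace study day with off-treatment day, defined as entry date minus date of last IMP intake in that period, and summarise Days 1 to 14.
2. Attribute each entry to the treatment of the period just ended.
3. Flag entries made after the first dose of the next period. That dose is taken in the evening, so an entry on the same date may precede it; if no entry time is available, mark its timing as undetermined rather than discard it.

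Separate displays for early stoppers and completers are optional.

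The cost is one derived variable and a few lines of SAP text. Last-intake dates per period are already used for exposure in SAP 4.10.1, and no new data collection is needed.

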4.12.11 Data Safety Monitoring Board (DSMB)

An independent Data Safety Monitoring Board (DSMB) will periodically review safety data. The frequency of data review and DSMB processes are outlined in the DSMB charter.

4.13 Other Analyses

Not Applicable

4.14 Determination of Sample Size

Original Sample size assumptions

The planned sample size of 44 subjects (22 per sequence) provides at least 80% power to detect a 40% reduction in Day 22 daytime cough frequency (coughs per hour) with NAL ER tablet treatment compared to placebo tablets at the 5% significance level (2-sided). This assumes a CV of 1.00 in log-transformed Day 22 cough frequencies. The CV estimated from Kelsall et al (2011) data on chronic cough in patients without esophageal catheterization is 1.12; because Kelsall et al data was on 24-hour cough (including nighttime cough, a period of lower coughing rate) and were not taken in a sample of IPF patients only, it is believed that the CV will be lower than in Kelsall et al data. If the CV is larger than planned at 1.25, this sample size provides > 80% power to detect a 34% reduction from placebo to NAL ER.

A total of approximately 60 subjects will be randomized to ensure complete data from at least 44 subjects, assuming up to potentially a 26% dropout rate.

Study early interruption

As described in this SAP at sections 4.11.1.5 and 4.15, study was terminated before reaching the total sample size.

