11.1 Sample Size and Power

The planned sample size of 44 subjects for the final analysis (22 per sequence) provides at least 80% power to detect a 40% reduction in Day 22 daytime cough frequency (coughs per hour) with NAL ER tablet treatment compared to placebo tablets at the 5% significance level (2-sided). This assumes a CV of 1.00 in log-transformed Day 22 cough frequencies. The CV estimated from *Kelsall et al (2011)* data on chronic cough in patients without esophageal catheterization is 1.12; because Kelsall et al data was on 24-hour cough (including nighttime cough, a period of lower coughing rate) and were not taken in a sample of IPF patients only, it is believed that the CV will be lower than in Kelsall et al data. If the CV is larger than planned at 1.25, this sample size provides > 80% power to detect a 50% reduction from placebo to NAL ER. Alternatively, if the CV is 0.75, this sample size provides > 80% power to detect a 34% reduction from placebo to NAL ER.

A total of approximately 60 subjects will be randomized to ensure complete data from at least 44 subjects, assuming up to potentially a 26% dropout rate.

A statistical update on this Proof-of-Concept (POC) study may be conducted when a minimum of 12 subjects have completed both study periods for the purposes of determining whether POC can be established prior to complete enrollment of the study.

The analysis will be based on conditional power (CP). Futility will be declared if the CP is < 10%, while efficacy will be declared if the CP > 80% (*Mehta and Pocock, 2010*). If the CP is at least 41%, the number of subjects per treatment arm may be changed to recover the targeted power of 80%. If it is evident that the outcome is influenced by a baseline imbalance in disease characteristics then the baseline imbalance will be taken into account in supplemental analyses.

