3 INVESTIGATIONAL PLAN

3.1 Overall Study Design and Plan

This is a double-blind, randomized, placebo-controlled, 2-treatment, 2-period crossover efficacy and safety study in IPF subjects with NAL ER tablets for the treatment of cough.

The study consists of 2 treatment periods of 3 weeks, each followed by a washout period of 2 weeks.

During Treatment Period 1, eligible subjects will be randomized (1:1) to one of the following treatment arms:

- Arm 1: Active NAL ER tablets followed by crossover Placebo tablets in Treatment Period 2
- Arm 2: Placebo tablets followed by crossover NAL ER tablets in Treatment Period 2

Following 3 weeks of dosing in Treatment Period 1, subjects will complete a 2-week washout period before entering Treatment Period 2. Subjects assigned to Arm 1 will receive placebo tablets and subjects assigned to Arm 2 will receive NAL ER tablets during Treatment Period 2. A final 2-week washout period will occur at the completion of Treatment Period 2.

Subjects on NAL ER tablets will have the dose titrated from 27 mg once daily (QD) to 54 mg BID over a 5-day period and then maintained at 54 mg BID for approximately 4 days. Doses will be subsequently escalated and maintained at 108 mg BID over 1 week and then to 162 mg BID over 6 days.

Study visits will include screening to determine eligibility, and for each treatment period: visits at Day -1 for baseline assessments, at Days 8, 15, and 21 during treatment, and a follow-up at the end of the 2-week washout period. At study screening and the Day 21 visits during each treatment period, subjects will have blood drawn for safety analysis. Nalbuphine (and/or metabolites) plasma concentration will also be measured at Day 21. Subjects will complete questionnaires for efficacy evaluations and undergo safety evaluations including an ECG. At the baseline and Day 21 visits, during each treatment period, site staff will place an electronic cough monitor on the subject, which will be worn until the evening of the following day in order to obtain at least a full 24-hour recording period of cough frequency. At the end of each recording session, the monitor will be removed at home by the subject prior to bedtime. Subjects will complete a daily e-diary twice per day.

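### SAP 4.14 claims more than 80% power for a 34% reduction at CV 1.25; with 44 completers it is about 50%, and the protocol claims something different

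*SAP*

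**What the plan says.** SAP 4.14 starts from the base case: "The planned sample size of 44 subjects (22 per sequence) provides at least 80% power to detect a 40% reduction", with a two-sided 5% test. On variability it says: "This assumes a CV of 1.00 in log-transformed Day 22 cough frequencies". It then gives a single sensitivity statement: "If the CV is larger than planned at 1.25, this sample size provides > 80% power to detect a 34% reduction".

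Protocol 11.1 has the same base case but two sensitivity statements. The first is "If the CV is larger than planned at 1.25, this sample size provides > 80% power to detect a 50% reduction". The second, for lower variability, is "if the CV is 0.75, this sample size provides > 80% power to detect a 34% reduction". The protocol synopsis repeats both. The 50% reduction and the CV of 0.75 appear nowhere in SAP 4.14.

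The SAP's introduction names protocol version 7.0 as its basis, and that version contains both statements. SAP 4.15, on changes to the planned analysis, records no change to the power scenarios.

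**The concern.** The SAP sentence does not fit the one before it. With sample size and test fixed, raising the CV from 1.00 to 1.25 raises the smallest reduction that can be detected with 80% power. The SAP has it falling from 40% to 34%. That could be true only if the base case had a great deal of power to spare, and it has almost none.

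The error lies in the direction that matters. Both documents cite an external CV estimate of 1.12, above the planned 1.00, so a CV higher than planned is a realistic case. A reader of the SAP, or of a study report that takes its sample-size text from there, would believe that the trial could reliably detect a 34% reduction under high variability. In that setting it is close to a coin toss, and a non-significant result could be taken as stronger evidence against a 34% effect than it is.

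**Working it through.** **Inputs**
- Design: "2-treatment, 2-period crossover efficacy and safety study in IPF subjects", allocated 1:1 to sequence (SAP 3.1).
- Completers: N = 44, 22 per sequence (SAP 4.14, Protocol 11.1).
- Test: two-sided, alpha 0.05 (SAP 4.14).
- CV and reduction pairs: as stated in SAP 4.14 and Protocol 11.1.
- Assumption: the CV is the within-subject CV on the original scale. The documents attach it to log-transformed frequencies and do not say whether it is within-subject.

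**Formulas**
- Log-scale within-subject SD: s = sqrt(ln(1 + CV²))
- Standard error of the treatment difference: SE = s × sqrt(2/44) = 0.2132 × s
- Effect: d = |ln(1 − reduction)|
- Power: non-central t with 42 df and non-centrality d/SE

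**The plan's own scenarios first, then the SAP pair**

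| Scenario | s | SE | d | d/SE | Power | Claimed |
|---|---|---|---|---|---|---|
| Base case: CV 1.00, 40% | 0.8326 | 0.1775 | 0.5108 | 2.878 | 0.803 | at least 0.80 |
| Protocol: CV 1.25, 50% | 0.970 | 0.2068 | 0.6931 | 3.352 | 0.906 | > 0.80 |
| Protocol: CV 0.75, 34% | 0.668 | 0.1424 | 0.4155 | 2.917 | 0.813 | > 0.80 |
| SAP: CV 1.25, 34% | 0.970 | 0.2068 | 0.4155 | 2.009 | **0.501** | > 0.80 |

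The first three claims hold. In the base case 44 is also the smallest even total that reaches 80%, so the formula is very probably the one behind the plan. Only the SAP pair fails. The normal approximation gives 0.520 for it.

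**What CV 1.25 would allow**
- Smallest reduction detectable with 80% power at N = 44: 44.7% (44.0% by the normal approximation).
- Completers needed for 80% power at a 34% reduction: 88 (86 by the normal approximation), twice the plan.

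**Other readings of the inputs for the SAP pair**

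| Reading | SAP pair | Base case |
|---|---|---|
| One-sided test (normal approximation) | 0.642 | 0.891 |
| Parallel groups, 22 per arm | 0.284 | 0.511 |
| CV taken directly as the log SD | 0.332 | 0.648 |
| CV taken as the SD of the within-subject difference | 0.577 | 0.912 |
| s taken as the SD of the within-subject difference | 0.793 | 0.978 |
| All 60 randomized complete | 0.636 | 0.911 |

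None brings the SAP pair to 80%. The nearest, 0.793, would put the base case at 0.978, so it cannot be how 44 was chosen.

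**The case against.** The arithmetic is not in dispute. The case on the other side is about cause, precision and consequence.

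- **Cause.** That two sentences were merged is inferred. The missing text runs between two occurrences of the same phrase, which is where a copyist skips a line, but a fault in PDF text conversion could do the same. This stands as a caution, and the signed page is worth a look before editing. Against it, the SAP sentence is complete and grammatical.
- **Precision.** The figures of 0.50, 88 and 45% depend on how the CV is read. This stands, and the assumption has to be stated. The conclusion does not depend on it, because every reading tried falls below 80%. It is also fair that the base case claims at least 80%, so the contradiction is not proved by the wording alone. The calculated 0.803 closes that gap.
- **Consequence.** The sentence sits under the subheading for the original assumptions. Recruitment ended with subjects randomized on or before 11 March 2022, and the SAP was signed on 8 June 2022, so no sizing decision could rest on it. No analysis or decision rule uses the figure, and the primary result is reported with a confidence interval (SAP 4.11.2), which is the proper basis for reading a null result. This largely stands. It limits the harm to a misleading account of the design's robustness.

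**Conclusion.** The point holds. SAP 4.14 states a power above 80% where the value is about 50%, and it contradicts the protocol on which it is based. The value of 0.50 assumes a within-subject CV on the original scale, 44 completers and a two-sided 5% test. Other readings give 0.28 to 0.79, all below the claim. The protocol's two scenarios are both correct. The base case, the 44 completers, the 60 randomized and the primary analysis are untouched. This is a substantive error in a stated figure, with limited practical consequence because enrolment had closed. It should be corrected.

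**What to change.** In SAP 4.14, delete the merged sentence and restore the protocol's two statements: at CV 1.25, more than 80% power for a 50% reduction; at CV 0.75, more than 80% power for a 34% reduction. It would help to add that at CV 1.25 a reduction of about 45% is detectable with 80% power (computed 0.806 at 45%). That figure is in neither document, so it should be given with its CV assumption. If the SAP is not reissued, make the correction where the study report describes the sample size.

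The cost is one edit and no new analysis. The stated robustness to a high CV becomes less favourable, as it should.
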